3.7.1.6 Open-label Stabilization Phase /Randomization/Early Termination

Subjects should be randomized at the visit where they meet the protocol-specified stabilization criteria; the visit where stabilization is confirmed will revert to the EOP visit. However, if for some reason subject was not randomized, if the subject still meets eligibility criteria at the next visit they can be randomized at that time. In those instances, the earlier assessment should be completed according to that week's required assessments, and not as an EOP visit.

The subject will return to the clinic for a visit at Week 20 (± 3 days) during the open-label stabilization phase. Investigators must perform the open-label stabilization phase assessments to determine if the subject has maintained the stabilization criteria for entry into the double-blind randomized withdrawal phase. The EOP visit must serve as the baseline for double-blind randomized withdrawal phase; therefore, all evaluations noted for Week 20/EOP or ET must be performed on the day of randomization prior to the first dose of double-blind IMP. Randomization ([Section 3.7.1.6.1](#)) must occur on the same day that the subject receives double-blind IMP for double-blind randomized withdrawal phase.

The following procedures are to be completed at the Week 20/EOP visit:

- 1) Current psychotropic therapy will be recorded.
- 2) The YGTSS and CGI-TS (severity and improvement assessments) will be performed to assess symptoms associated with TD.
- 3) Completion of the C-SSRS (children's version).
- 4) For all FOCBP and sexually active males, documentation of birth control methods will be completed. Abstinence is permitted if it is confirmed and documented at every visit.

Protocol 31-14-204

- 5) AEs and concomitant medications will be recorded.
- 6) Drug accountability records will be completed.
- 7) Stability will be assessed.
- 8) A complete physical examination will be performed.
- 9) Height, body weight, and waist circumference will be measured.
- 10) A urine pregnancy test will be done on FOCBP.
- 11) Urine drug and blood alcohol screens will be done.
- 12) The SAS, BARS, and AIMS will be administered. Benztropine (up to 4 mg/day) is not to be administered 12 hours prior to rating scales. Benzodiazepines (up to 3 mg/day lorazepam equivalents) are not to be administered 4 hours prior to rating scales.

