3.7.2.2 Clinical Global Impression Scale for Tourette's Syndrome

The severity of illness and efficacy of IMP for each subject will be rated using the CGI-TS scale.¹⁴ To assess CGI-TS severity, the rater or investigator will answer the following question: "Considering your total clinical experience with this particular population, how mentally ill is the patient at this time?" However, the evaluation of illness will be limited to manifestations of TD only. Response choices include: 0 = not assessed; 1 = normal, not at all ill; 2 = borderline mentally ill; 3 = mildly ill; 4 = moderately ill; 5 = markedly ill; 6 = severely ill; and 7 = among the most extremely ill patients.

The rater or investigator will rate the subject's total improvement whether or not it is due to drug treatment. All responses will be compared to the subject's condition at baseline (Day 1). Response choices include: 0 = not assessed, 1 = very much improved, 2 = much improved, 3 = minimally improved, 4 = no change, 5 = minimally worse, 6 = much worse, and 7 = very much worse.

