7.4.3.2 Double-blind Randomized Withdrawal Phase

Exploratory efficacy endpoints during the double-blind randomized withdrawal phase include:

- Mean change from randomization to last visit (Week 12 for completers and withdrawal visit for discontinued subject) in YGTSS TTS score
- Mean change from randomization to last visit (Week 12 for completers and withdrawal visit for discontinued subject) in Total YGTSS score
- Mean change from randomization to last visit (Week 12 for completers and withdrawal visit for discontinued subject) in CGI-TS Severity score
- CGI-TS Improvement score at last visit (Week 12 for completers and withdrawal visit for discontinued subject)

For the above endpoints except the CGI-TS Improvement score, randomization baseline is defined as the assessment taken at the last visit of the open-label stabilization phase prior to the first dose of the randomized IMP.

Variables in the form of change from randomization baseline will be analyzed using mixed model repeated measures (MMRM) under the assumption of missing at random (MAR). The time variable is scheduled visits, which will be treated as a categorical repeated factor. The MMRM model will include terms of treatment, visit, and treatment by visit interactions as fixed categorical effects, baseline as well as baseline by visit interactions as covariates, and a single unstructured covariance matrix assumed for all treatment arms in the model. Restricted maximum likelihood estimates of the treatment difference, their 2-sided 95% CIs and p-values (using Kenward-Roger degrees of freedom) from the MMRM inference will be provided.

The change from randomization baseline to Week 12 of the double-blind randomized withdrawal phase in the above variables will also be analyzed using analysis of covariance (ANCOVA) with missing data being imputed by last observation carried

Protocol 31-14-204

forward. The ANCOVA model will include treatment as a factor and baseline value as a covariate.

To evaluate the sensitivity of the results to missing data that are potentially missing not at random (MNAR), sensitivity analyses will be conducted with multiple imputations for missing data under the assumption of MNAR, which will be detailed in the SAP.

CGI-TS Improvement score from postbaseline visits will be analyzed in a similar fashion to those change from baseline variables except that there will not be adjustment for baseline value in the analyses of CGI-TS Improvement score.

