5.2 Definition of Baseline and Last Visit

Baseline for Open-label Stabilization Phase is defined as the last visit with available data prior to the first dose in Open-label Stabilization Phase. Last visit in Open-label Stabilization Phase is defined as the last visit with available data prior to randomization, or on/before early termination in the Open-label Stabilization Phase.

Baseline for Double-blind Randomized Withdrawal Phase is defined as the last visit of the Open-label Stabilization Phase prior to the first dose of double-blind IMP in Double-blind Randomized Withdrawal Phase. Last visit in Double-blind Randomized Withdrawal Phase is defined as the last visit with available data at the completion or on/before early termination for the randomized subjects.

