8.1 Primary Efficacy Endpoint

8.1.1 Primary Endpoint Analysis

The primary endpoint is time from randomization to relapse during the double-blind randomized withdrawal phase. Relapse is defined as a loss of $\geq 50\%$ of the improvement experienced during the open-label stabilization phase (i.e., improvement at the last

assessment of YGTSS before randomization) on the YGTSS TTS. Since this trial has terminated early due to withdrawal of postmarketing commitment (PMC), only relapse rate will be provided by treatment group for ITT sample.

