8.2 Exploratory Efficacy Endpoints

8.2.1 Exploratory Efficacy Endpoints Analysis

Descriptive statistics for the following efficacy endpoints will be provided by trail week and last visit for open-label efficacy sample in open-label stabilization phase and ITT sample in double-blinded randomized withdrawal phase, respectively.

- Change from randomization to last visit in YGTSS TTS score;
- Change from randomization to last visit in Total YGTSS score;
- Change from randomization to last visit in CGI-TS Severity score;
- CGI-TS Improvement score at last visit.

The YGTSS is a semi-structured clinical interview designed to measure current tic severity. This scale consists of a tic inventory, with 5 separate rating scales to rate the severity of symptoms, and an impairment ranking. Ratings are made along 5 different dimensions on a scale of 0 to 5 for motor and vocal tics, each including number, frequency, intensity, complexity, and interference. Summation of these scores (i.e., 0-50) provides a YGTSS-TTS score. The YGTSS ranking of impairment with a maximum of 50 points, is based on the impact of the tic disorder on areas of self-esteem, family life, social acceptance, and school scores. Total YGTSS score is sum of YGTSS-TTS score and impairment score with range of 0 to 100.

The severity of illness and efficacy of IMP for each subject will be rated using the CGI-TS scale. Response choices include: 0 = not assessed; 1 = normal, not at all ill; 2 = borderline mentally ill; 3 = mildly ill; 4 = moderately ill; 5 = markedly ill; 6 = severely ill; and 7 = among the most extremely ill patients. The rater or investigator will rate the subject's total improvement whether it is due to drug treatment. All responses will be compared to the subject's condition at baseline. Response choices include: 0 = not assessed, 1 = very much improved, 2 = much improved, 3 = minimally improved, 4 = no change, 5 = minimally worse, 6 = much worse, and 7 = very much worse.

9 Safety Analyses

Safety analysis will be conducted based on open-label and randomized safety samples, which are defined in [Section 5.1](#). Safety variables to be analyzed include AEs, clinical laboratory tests, physical examinations, vital signs, ECGs, suicidality via the C-SSRS (children's version). In general, safety data will be summarized using descriptive

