9.6.2 Suicidality

The incidence of suicidality, suicidal behavior and suicidal ideation will be calculated from the potential suicide events recorded on the C-SSRS (children's version) in the single-blind stabilization phase and double-blind randomized withdrawal phase for the safety samples. Suicidality will be assessed based on C-SSRS data. Data for the Baseline Version of the C-SSRS and Since Last Visit Version of the C-SSRS data will be summarized descriptively and presented in a listing.

The baseline version of C-SSRS is administered at the screening visit and the "Since Last Visit" version is administered at all subsequent visits. Baseline and post-baseline C-SSRS data will be summarized to report the incidence of suicidality, suicidal behavior and suicidal ideation. Suicidality is defined as reporting at least 1 occurrence of any suicidal behavior or suicidal ideation. Suicidal behavior is defined as reporting any type of suicidal behaviors. Suicidal ideation is defined as reporting any type of suicidal ideation.

In addition, C-SSRS data collected post-baseline will also be summarized to report the incidence of completed suicide, emergence of suicidal ideation, emergence of serious suicidal ideation, worsening of suicidal ideation and emergence of suicidal behavior. Any completed suicide is considered as complete suicidality. Emergence of suicidal ideation is defined as having no suicidal ideation at screening and baseline and reporting any type of ideation during treatment. Emergence of serious suicidal ideation is defined as having no suicidal ideation at screening and baseline and reporting any type of suicidal ideation with ideation severity rating of 4 or 5 during treatment. Worsening of suicidal ideation is defined as occurring when the most severe suicidal ideation rating during treatment is more severe than its worst rating at screening and baseline. Emergence of suicidal behavior is defined as having no suicidal behavior at screening and baseline and reporting any type of suicidal behavior during treatment.

10 Pharmacokinetic Analyses

None.

11 Pharmacodynamic Analyses

None.

12 Pharmacogenomic Analyses.

None.

13 Interim Analysis

None.

14 Changes in the Planned Analyses

This trial was terminated due to withdrawal of postmarketing commitment, so the interim analysis specified in the protocol was not to be conducted. The descriptive statistics will be provided for all the efficacy endpoints.

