Appendix 4 Proposed Summary Tables and Data Listings

Proposed Summary Tables:

- CT-1.1.1 Subject Disposition by Phase
- CT-1.1.2 Subject Disposition in Double-Blind Randomized Withdrawal Phase (Randomized Sample)
- CT-1.2.1 Subject Enrollment by Region, Country and Center
- CT-1.2.1 Subject Enrollment by Region, Country and Center (Randomized Sample)
- CT-1.3.1 Subject Enrollment by Age Group at Enrollment
- CT-1.3.2 Subject Enrollment by Age Group at Enrollment (Randomized Sample)
- CT-2.1 Reasons for Discontinuation by Phase (Enrolled Sample)
- CT-2.2 Reasons for Discontinuation (Randomized Sample)
- CT-3.1.1 Demographic Characteristics (Enrolled Sample)
- CT-3.1.2 Demographic Characteristics (Randomized Sample)
- CT-3.2.1 Baseline Disease Characteristics (Enrolled Sample)
- CT-3.2.2 Baseline Disease Characteristics (Randomized Sample)
- CT-4.1 Concomitant Medications: Medications Taken by Phase (Open-Label Safety Sample)
- CT-4.2.1 Concomitant Medications: Medications Taken Prior to Start of Study Therapy (Randomized Safety Sample)
- CT-4.2.2 Concomitant Medications: Medications Taken During Open-Label Stabilization Phase (Randomized Safety Sample)
- CT-4.2.3 Concomitant Medications: Medications Taken During Double-Blind Randomized Withdrawal Phase (Randomized Safety Sample)
- CT-4.2.4 Concomitant Medications: Medications Taken Post Study Therapy Period (Randomized Safety Sample)
- CT-5.1 Descriptive statistics for Relapse Rate (ITT Sample)
- CT-5.2.1 Yale Global Tic Severity Scale - Total Tic Score (YGTSS - TTS) - Mean Change from Baseline by Week - OC (Open-Label Efficacy Sample)
- CT-5.2.2 Yale Global Tic Severity Scale - Total Tic Score (YGTSS - TTS) - Mean Change from Baseline by Week - OC (ITT Sample)
- CT-5.3.1 Total Yale Global Tic Severity Scale Score - Mean Change from Baseline by Week - OC (Open-Label Efficacy Sample)
- CT-5.3.2 Total Yale Global Tic Severity Scale Score - Mean Change from Baseline by Week - OC (ITT Sample)
- CT-5.4.1 Clinical Global Impressions Scale for Tourette's Syndrome (CGI-TS) Severity score - Mean Change from Baseline by Week - OC (Open-Label Efficacy Sample)
- CT-5.4.2 Clinical Global Impressions Scale for Tourette's Syndrome (CGI-TS) Severity score - Mean Change from Baseline by Week - OC (ITT Sample)
- CT-5.5.1 Clinical Global Impressions Scale for Tourette's Syndrome (CGI-TS) Improvement Score - Mean by Week - OC (Open-Label Efficacy Sample)

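### Should CGI-TS Improvement in the double-blind phase be adjusted for, or shown as change from, the rating made at the randomization visit?

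*Protocol*

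**What the plan says.** **Protocol.** Section 7.4.3.2 gives YGTSS TTS, Total YGTSS and CGI-TS Severity a randomization baseline. That value enters the MMRM as a covariate with its visit interaction, and enters the ANCOVA as a covariate. CGI-TS Improvement is excepted from the baseline definition and again from the models: "there will not be adjustment for baseline value in the analyses of CGI-TS Improvement score". Section 3.7.2.2 has the rater compare each response with the subject's "condition at baseline (Day 1"). Section 3.7.1.6 includes the Improvement rating in the end-of-phase (EOP) visit and requires that "all evaluations noted for Week 20/EOP or ET must be performed on the day of randomization prior to the first dose of double-blind IMP".

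**SAP.** Section 5.2 states: "Baseline for Double-blind Randomized Withdrawal Phase is defined as the last visit of the Open-label Stabilization Phase", with no exception for Improvement. Section 8.2.1 compares the rating with the subject's "condition at baseline. Response choices include: 0 = not assessed, 1 = very much improved", without naming Day 1. For the primary endpoint, Section 8.1.1 says that "only relapse rate will be provided by treatment group for ITT sample". Section 14 adds: "The descriptive statistics will be provided for all the efficacy endpoints". In Appendix 4, CT-5.4.2 is titled "Severity score - Mean Change from Baseline by Week - OC (ITT Sample"). CT-5.2.2 and CT-5.3.2 take the same form, while CT-5.5.2 (Improvement) is a mean by week only.

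**The concern.** Improvement scores are often left unadjusted because they are already change scores with no baseline value. That argument is weaker in a randomized-withdrawal design. Each double-blind rating carries the improvement gained in up to 20 open-label weeks, and a rating with the same Day 1 anchor is scheduled just before the first double-blind dose. Leaving it out of the model gives up precision and leaves the comparison open to chance differences between arms in open-label response.

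The tables raise a related worry. A reader of CT-5.5.2 sees weekly means with no starting value beside them. The SAP defines two baselines and does not say which one the rating refers to. One of the four exploratory results could then be harder to read than the rest.

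**Working it through.** **Inputs.** Planned size is 38 per arm (Protocol 7.1). This reproduces: 38 × 0.65 + 2 × 38 × 0.34 = 50.54, rounded up to the stated 51 events. The implied hazard ratio is ln(0.66)/ln(0.35) = 0.396. Pairwise power on 37.6 events at a hazard ratio of 0.4 is 80.2%, against the stated 80%. The documents give no figure for Improvement, so the correlation ρ between the EOP rating and a later rating is an assumption, shown over a range.

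**1. Precision, had the protocol model been run.** With three arms, 38 per arm and one covariate, adjusted variance ÷ unadjusted variance = (1 − ρ²) × (1 + 1/(3 × 37 − 2)) = (1 − ρ²) × 1.009.

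| ρ (assumed) | Variance ratio | SE reduction | Equivalent extra subjects (1/ratio − 1) |
|---|---|---|---|
| 0 | 1.009 | none | none |
| 0.3 | 0.918 | 4% | 9% |
| 0.5 | 0.757 | 13% | 32% |
| 0.7 | 0.515 | 28% | 94% |

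Simulation of 20,000 trials per value gave 1.006, 0.913, 0.749 and 0.514. Type I error was 4.9–5.1% with and without adjustment, and both estimates centred on zero. Precision is at issue, not validity.

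**2. Allowing for the scale.** The protocol requires at least 35% TTS improvement at the randomization visit, so EOP ratings cluster in the improved categories. With an assumed spread of 35/50/15% over categories 1/2/3, latent correlations of 0.3, 0.5 and 0.7 fall to 0.25, 0.44 and 0.61. The simulated variance ratios are then 0.942, 0.818 and 0.637. That is an SE reduction of 3%, 10% and 20%, equivalent to 6%, 22% and 57% more subjects.

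**3. Chance imbalance.** The standard deviation of an arm difference in EOP score is √(2/38) = 0.23 SD, so the 95% range is ±1.96 × 0.23 = ±0.45 SD. The part carried into the raw comparison is ρ × imbalance. At the edge of the range this is 0.13, 0.22 or 0.31 SD for ρ of 0.3, 0.5 or 0.7. At a typical imbalance and ρ = 0.25 it is 0.23 × 0.25 = 0.06 SD. The number actually randomized is not stated; with an assumed 20 or 10 per arm the range widens to ±0.62 or ±0.88 SD.

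**4. Would a change column read better?** With equal SDs, change-score variance ÷ raw variance = 2(1 − ρ), which is 1.4, 1.0 and 0.6 at ρ of 0.3, 0.5 and 0.7. In general, if k is the EOP SD over the later SD, the ratio is 1 + k² − 2ρk, and change is the less variable only when ρ > k/2. A restricted EOP spread lowers that threshold, but no fixed advantage for change can be claimed.

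**5. What reaches output.** SAP 8.2.1 and Section 14 give descriptive statistics for all efficacy endpoints and no MMRM or ANCOVA. Steps 1 and 2 therefore describe an analysis that will not be run.

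**6. The table against its endpoint.** Protocol 3.5.1.3 and SAP 6.3 define this endpoint as the score at the last visit and the other three as changes from randomization. Each table title follows its endpoint. Protocol 7.4.3.1 likewise summarizes only observed Improvement values in the open-label phase, and CT-5.5.1 does the same.

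**7. Is the starting value shown anywhere?** SAP 7.2 presents disease characteristics at baseline, including efficacy assessments, by phase and treatment group. With the double-blind baseline of SAP 5.2, that covers the randomization visit by arm. Improvement is neither named nor excluded. YGTSS and CGI-TS Severity by arm would also reveal unequal open-label response.

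**The case for a change.** The strongest case for a change is that the covariate is free. It is scheduled, measured before double-blind treatment, and anchored like the later ratings; if it proved useless, the ANCOVA variance would rise by only 0.9%. As a comment on the protocol model this stands, and any later analysis reusing that model would do well to include the rating. The gain could not simply be read across to the MMRM, though. The ANCOVA ratios apply there with complete data, whereas 51 of 114 subjects (45%) are expected to relapse and relapsers are to be discontinued.

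It can also be said that a few columns and a footnote in CT-5.5.2 cost almost nothing, that CT-3.2.2 does not name Improvement in its title, and that CT-5.5.1 includes subjects never randomized. All of this is true. But the columns would sit in one descriptive exploratory table, would not reliably be less noisy than the means already there, and would partly repeat the display planned in SAP 7.2.

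Two smaller points do not alter this. The reference for the rating is fixed by Protocol 3.7.2.2, and the SAP states that it is based on the protocol and its amendments, so the missing Day 1 creates no real doubt about what was rated. Neither document says to leave code 0 (not assessed) out of the means, but an analyst would treat it as missing without instruction.

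**Conclusion.** No change to the plan is needed. The protocol's exception is explicit, gives an unbiased comparison with correct type I error, and has no effect on the primary endpoint. Its cost would have been precision on one exploratory score: an SE about 3–4% larger than necessary at an assumed correlation of 0.3, in the sense of the reductions above, and about 10–13% at 0.5. The low end is plausible because all randomized subjects are responders. Under the SAP even that cost does not arise, since no efficacy model is fitted.

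The reporting point comes down to a table that matches its endpoint, a starting value that SAP 7.2 can reasonably be read to cover, and a dropped Day 1 that is clerical. The conclusion rests on the analysis staying descriptive. If the protocol's MMRM or ANCOVA were revived, using the randomization-visit rating as a covariate would be worth reconsidering.

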7.4.4 Interim Analysis

One IA is planned for the assessment of efficacy. The analysis will be performed following a group sequential approach at approximately 70% of events accrual time point and will include all randomized subjects. Subjects who withdraw early from the trial, or who are still in the trial at the end of trial without relapse, will be considered as censored observations. The O'Brien-Fleming boundaries will be used for the IA so that the IA will be conducted when 36 impending relapse events are available. The 2-sided alpha level for the IA is 0.016 and the alpha left for the final analysis will be 0.045 as specified in [Table 7.4.1-1](#). Additionally, a 95% CI for the hazard ratio (either aripiprazole or placebo) will be provided using the Cox proportional hazard model with term of treatment in the model.

If the null hypothesis on comparison between aripiprazole full dose and placebo is rejected at the IA time point, the trial will be terminated. An IA plan will be developed to document the details of the stopping rules, data flow and other logistical considerations relating to the IA.

7.5 Analysis of Demographic and Baseline Characteristics

Demographic and baseline characteristics will be summarized by descriptive statistics including tabulations of mean, median, range, and SD for continuous variables, and tabulations of frequency distributions for categorical variables. These summary statistics will be provided for the Open-label Safety Sample as well as by treatment groups for the ITT Sample.

Protocol 31-14-204

